3. STUDY DESIGN

This is an open-label, multicenter, randomized and controlled study. Approximately 25 investigational sites will be involved in US. Neonates will be evaluated according to the selection criteria and then randomized to surfactant treatment via LISA or standard administration procedure ([Table 1](#)). The enrollment will be staggered: the gestational age will be restricted to 27⁺⁰ weeks up to 28⁺⁶ completed weeks until safety evaluation by ISMB is performed for the first 15 neonates. Provided no safety concerns are raised, the enrollment will then be extended to the whole population (i.e. 25⁺⁰ weeks up to 28⁺⁶ completed weeks).

[figure not shown]
Enrolled neonates will be evaluated:

- until discharge,
- until 40 weeks PMA (if still in hospital),
- if discharge occurs before 36 weeks, the last evaluation will be at 36 weeks PMA.

This period represents the main phase of the trial.

Their final assessment of development will be at 24-month corrected age as a separate stand-alone visit. This 24-month clinical assessment will be analyzed and evaluated separately from the initial part of the study and will be object of an addendum to the initial core clinical study report.

Table 1: TIMETABLE

End of the trial

The end of the trial will correspond to the last evaluation of the last neonate from the recruiting site or from the continuing care site in case the treated baby was transferred from the original recruiting site. The last evaluation could be:

- the date of the assessment for BPD diagnosis (i.e. 36 weeks PMA) if the patient is discharged home before 36 weeks PMA,
- discharge home (if discharged between 36 weeks and 40 weeks PMA), or
- 40 weeks PMA (if still in hospital).

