8. EFFICACY ASSESSMENTS

The following variables will be used to describe the efficacy of the two procedures:

- Percentage of neonates needing invasive mechanical ventilation (MV) in the first 72 hours of life, 28 days PNA and within 36 weeks PMA defined as follows:

ETT group

- neonates not extubated within 1 hour from initial surfactant administration and receiving MV for more than 1 hour;
- neonates extubated and re-intubated to receive MV of any duration.

LISA group

- neonates intubated to receive MV of any duration,
 - Duration of invasive ventilation (hours) in the first 72 hours of life, 28 days PNA and within 36 weeks PMA;
 - Percentage of neonates needing any intubation procedure, outside the initial surfactant administration period, in the first 72 hours of life, in the first 28 days PNA and within 36 weeks PMA;
 - SpO₂ at time 0 (study treatment administration), 5, 15, 30 minutes, at 1, 6, 12, 24, 48, 72 and 120 hours post treatment; additionally, at 28 days PNA and at 36 weeks PMA for neonates still receiving any form of respiratory support;
 - FiO₂ at time 0 (study treatment administration), 5, 15, 30 minutes, at 1, 6, 12, 24, 48, 72 and 120 hours post treatment; additionally, at 28 days PNA and at 36 weeks PMA for neonates still receiving any form of respiratory

support;

- SpO₂/FiO₂ at time 0 (study treatment administration), 5, 15, 30 minutes, at 1, 6, 12, 24, 48, 72 and 120 hours post treatment; additionally, at 28 days PNA and at 36 weeks PMA for neonates still receiving any form of respiratory support;
- Percentage of neonates needing additional surfactant doses and number of surfactant doses;
- Duration of oxygen alone supplementation (days) and any non-invasive ventilation during the study (days);
- Blood gas analysis, specifically acid-base balance parameters (i.e. pH, pCO₂, pO₂, HCO₃, BE, lactate) pre-surfactant administration (when applicable), at 1 hour, 6 hours, 24, 48 and 72 hours after study treatment.

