effects and pre-procedure SpO₂/FiO₂ as covariate. The adjusted means in each treatment group, the adjusted mean difference between treatments and their 95% CIs at each time point and averaged over the first 120 hours post-treatment will be estimated by the model. Time profile plot of mean SpO₂/FiO₂ in the first 120 hours post-treatment will be presented by treatment group.

- SpO₂/FiO₂ will be summarized between treatments at 28±2 Days PNA and at 36 weeks PMA by means of descriptive statistics.

Blood gas analysis

- Acid-base balance parameters (i.e. pH, pCO₂, pO₂, HCO₃, BE, lactate) will be summarized by treatments group as absolute and change from pre-treatment values by means of descriptive statistics.

Use of additional surfactant doses

- The percentage of subjects requiring at least one additional surfactant dose will be compared by treatment group by means of a Fisher's exact test at 5% significance interval. Odds ratio (OR) and related exact 95% CI will be also provided. Subjects with pulmonary hemorrhage will be excluded from this summary.
- The number of additional surfactant doses will be summarized by treatment group by means of descriptive statistics.

Duration of ventilation/oxygen supplementation (alone)

- The median duration time of invasive mechanical ventilation in the first 72 hours of life (hours), in the first 28 days PNA and within 36 weeks PMA (days), stand-alone oxygen supplementation (days), non-invasive ventilation (days) will be compared between treatment groups by using the Mann-Whitney U-test.

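### Support durations are compared by a rank test that gives death no adverse value, and the NIV and oxygen counts end on a date that depends on discharge

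*Protocol*

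**What the plan says.** Section 8 of the Protocol defines the invasive-ventilation variable as "Duration of invasive ventilation (hours) in the first 72 hours of life, 28 days PNA and within 36 weeks PMA". It counts stand-alone oxygen, and "any non-invasive ventilation during the study (days"), over the study rather than over a fixed window. Section 12.3.4 takes up the same invasive-ventilation windows, as "The median duration time of invasive mechanical ventilation in the first 72 hours of life (hours), in the first 28 days PNA and within 36" (the last in weeks PMA). It also fixes the test: oxygen days and "non-invasive ventilation (days) will be compared between treatment groups by using the Mann-Whitney U-test", as will the invasive-ventilation durations. Section 12.2 puts every randomised and dosed neonate in the efficacy analysis, so those who later die are included.

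Death enters the plan in Section 12.3.5, as mortality at Day 28 and 36 weeks PMA and within death/BPD. Neither Section 8 nor Section 12.3.4 says how a death enters a duration. Section 12.3.2 leaves missing data and outliers to the SAP.

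Section 3 gives three ends of evaluation. For early discharge, "if discharge occurs before 36 weeks, the last evaluation will be at 36 weeks PMA". For later discharge it is "discharge home (if discharged between 36 weeks and 40 weeks PMA"). Otherwise evaluation runs "until 40 weeks PMA (if still in hospital").

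**The concern.** A rank test on time spent on support treats a shorter time as better. Support can end because the infant recovers or because the infant dies, and the raw duration does not tell the two apart. A neonate ventilated until death on day 2 scores 2 days and ranks ahead of a survivor extubated on day 10 in the 28-day and 36-week windows. The protocol counts death as a failure in death/BPD but not here.

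The second problem is the counting window for NIV and oxygen. From 36 weeks PMA it closes at discharge or at 40 weeks, so its length depends on something that happens after randomisation and reflects recovery.

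Duration of invasive and non-invasive ventilation is named in the secondary objective (Section 2.2). A difference in mortality, or in discharge on support, would carry into that comparison.

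**Working it through.** **No figure to reproduce.** The protocol states no expected mortality, duration, effect size or power for these variables. Only the allocation can be checked: 150 × 2/3 = 100 and 150 × 1/3 = 50.

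**Direction of the effect of deaths.** Let a and b be mortality in LISA and control. Suppose survivors' durations have the same distribution in both arms, and so do the durations of those who die. Let q be the probability that a neonate who dies has a shorter duration than a survivor (ties count half). Then

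P(LISA shorter) = 0.5[(1−a)(1−b) + ab] + a(1−b)q + (1−a)b(1−q) = 0.5 + (a − b)(q − 0.5).

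With deaths ranked worst, q = 0 and P = 0.5 − 0.5(a − b). So:
- if a = b, both versions give 0.5;
- if q is between 0 and 0.5, the raw test keeps the right direction but is diluted;
- if q exceeds 0.5, the raw test favours the arm with more deaths.

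**NIV days (assumed).** Survivors: median 25 days, log-SD 0.7, capped at 91 days. Deaths: uniform over the first 14 days. Control mortality: 5%. These assumptions give q of about 0.94. Simulation used 3,000 trials of 100 v 50 at two-sided 5%.

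| LISA mortality | P raw, formula | P raw, simulated | P deaths worst, simulated | Raw test significant for LISA (nominal 2.5%) |
|---|---|---|---|---|
| 5% | 0.500 | 0.500 | 0.499 | 2.3% |
| 10% | 0.522 | 0.522 | 0.475 | 6.6% |
| 15% | 0.544 | 0.545 | 0.451 | 13.5% |
| 20% | 0.566 | 0.567 | 0.426 | 26.6% |
| 25% | 0.588 | 0.590 | 0.400 | 44.0% |

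For example, at 15%: 0.5 + (0.15 − 0.05)(0.94 − 0.5) = 0.544.

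**Invasive ventilation (assumed).** Two sets of inputs were tried, each with those who die ventilated until death.
- Half never ventilated, the rest median 5 days (log-SD 1.0), deaths uniform over 14 days, control mortality 5%. Here q is about 0.22. At LISA mortality 10/15/20%, simulated P is 0.485/0.473/0.458 raw and 0.474/0.450/0.425 with deaths worst. By formula at 20%: 0.5 + 0.15 × (0.22 − 0.5) = 0.458.
- 45% ventilated, median 7 days (log-SD 1), deaths at 0.5 to 7 days. A death then ranks worse than about 66% of survivors, so q is about 0.34. At 5% LISA v 15% control mortality, P = 0.5 + (−0.10)(−0.16) = 0.516 raw and 0.550 with deaths worst. The simulated rejection rate is about 6–7% raw and 19–20% with deaths worst.

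Both sets show dilution, not reversal.

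**Counting window for NIV and oxygen.** At 25+0 weeks, 36 weeks PMA is day (36 − 25) × 7 = 77 and 40 weeks is day 105. At 28+6 weeks they are days 50 and 78. By Section 3:

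| Infant | Counting ends |
|---|---|
| Discharged before 36 weeks | 36 weeks PMA |
| Discharged between 36 and 40 weeks | discharge |
| Still in hospital | 40 weeks PMA |

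The window therefore varies by up to 4 weeks (28 days). With the same history up to 37 weeks, an infant sent home on support at 37 weeks stops accruing and ranks ahead of one weaned in hospital at 38 weeks. It still ranks behind an infant weaned at 33 weeks.

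**The case against.** **The SAP may settle it.** The protocol names variables and a test. It does not say that a duration cut short by death is used unadjusted, and a reader who infers an explicit rule goes beyond the text. A SAP rule is possible. However, the deferral in Section 12.3.2 covers missing data and outliers, and time on support until death is fully observed. Followed as written, the definition and test give that value no other treatment.

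**Early death need not beat recovery.** A reader might infer that an early death outranks any recovered survivor. It does not: a survivor never ventilated has zero hours and ranks ahead of every ventilated death, and so does one weaned earlier. In the 72-hour window survivors are capped at 72 hours, which limits the gap. This part of the objection stands.

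**Discharge does not always stop the count.** A reader might infer that NIV and oxygen always stop at discharge. Section 3 follows infants discharged before 36 weeks to 36 weeks, Section 7.2.3 requires a visit then if they went home on support, and Section 7.1.7 collects the dates. Only discharge between 36 and 40 weeks shortens the count.

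**The events are visible elsewhere.** Mortality, death/BPD and respiratory support at discharge or 40 weeks are all reported. That limits the harm, but it does not correct the p-value of the duration test.

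**Worst-rank support-free time answers a different question** and can be driven by deaths. This is a fair cost, so raw durations should be kept as description.

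**Conclusion.** The point holds in limited form. As written, the duration comparisons rank an early death on support ahead of any survivor supported longer, so unequal mortality distorts them. For invasive ventilation the effect under both sets of assumptions is dilution. For NIV it can be reversal: P(LISA shorter) of 0.545 raw against 0.451 with deaths worst, at 15% v 5% mortality. With equal mortality there is no effect.

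Every size rests on assumed mortality and durations. The 64 deaths per 1000 live births in Section 1.1 is background and not an expected trial rate. It therefore cannot support an inference that a particular LISA benefit would be hidden.

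The variable end of the NIV and oxygen window is a separate, smaller defect of up to four weeks. No size was calculated for its effect on the test.

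Importance is modest: the study calls itself explorative (Section 1.1), defines no primary efficacy endpoint (Section 12.1) and compares mortality separately.

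**What to change.** In Sections 8 and 12.3.4, and in the SAP:
- Keep the Mann-Whitney test, but apply it to support-free time within 72 hours of life, 28 days PNA and 36 weeks PMA, with death inside the window ranked worst.
- For NIV and stand-alone oxygen, end the count at 36 weeks PMA instead of at the end of the study, and include support at home up to that date. All neonates are to be evaluated then. The length of the window depends on gestational age, a stratification factor at randomisation, and not on outcome.
- Do not count time on a higher level of support as NIV-free or oxygen-free. Otherwise a move from NIV to invasive ventilation would look like an improvement.
- Report raw durations in survivors, and support from 36 to 40 weeks, descriptively.

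The cost is wording and a derived variable. Support start and stop dates and the date of death are already collected, so no new data are needed. The downside is that the tested result reads as support-free time including death and not as plain hours or days. If the SAP already contains such a rule, the protocol wording should be aligned with it.

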	
 • Weight, OFC and length at discharge home or 40 weeks PMA will be summarized by treatment group by descriptive statistics. • Percentage of neonates needing invasive or non-invasive respiratory support at discharge home or 40 weeks PMA will be summarized by treatment group by frequency distribution • Neonates needing respiratory medications at discharge home or 40 weeks PMA will be summarized by treatment group by frequency distribution • Bayley Scales of Infant Development (BSID) (cognitive and language scores) will be summarized using descriptive statistics by treatment group and BSID version (III or IV). • Vital signs and all other variables collected through the questionnaire (i.e., anthropometric measures, cerebral palsy, seizures, feeding method, functional disability and respiratory morbidity) will be summarized by treatment group by frequency distribution or descriptive statistics as appropriate.
Statistical methods	Efficacy variables 
 • Percentage of neonates needing invasive mechanical ventilation in the first 72 hours of life, in the first 28 days PNA and within 36 weeks PMA will be compared between groups using the Cochran-Mantel-Haenszel (CMH) test adjusted for gestational age group. The CMH adjusted difference with its 95% confidence interval (CI) will be presented. Additional analysis will be performed to explore the impact of use of sedation and/or analgesia. • Duration of invasive mechanical ventilation in the first 72 hours of life, in the first 28 days PNA and within 36 weeks PMA will be compared between treatment groups by using the Mann-Whitney U-test. • Percentage of neonates needing any intubation procedure, outside the initial surfactant administration period, in the first 72 hours, in the first 28 days PNA and within 36 weeks PMA will be compared between treatment as need for invasive mechanical ventilation. • SpO₂ will be analysed using a linear mixed model for repeated measures (MMRM) including treatment, time point, treatment by time point interaction, and gestational age group as fixed effects and pre-procedure SpO₂ as covariate. The adjusted means in each treatment group, the adjusted mean difference between treatments and their 95% CIs at each time point and averaged over the first 120 hours post treatment will be estimated by the model. Time profile plot of mean SpO₂ in the first 120

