	
hours post-administration will be presented by treatment group.
 
• SpO₂ will be summarized by treatments on neonates still receiving respiratory support at 28±2 PNA, and at 36 weeks PMA using descriptive statistics.• FiO₂ will be analyzed as SpO₂.• SpO₂/FiO₂ will be analyzed as SpO₂.• Percentage of subjects requiring at least one additional surfactant dose will be compared by treatment group by means of a Fisher's exact test at 5% significance interval. Odds ratio (OR) and related exact 95% CI will be also provided. Subjects with pulmonary hemorrhage will be excluded from this summary.
Statistical methods	
• Number of additional surfactant doses will be summarized by treatment group by means of descriptive statistics.• Duration of stand-alone oxygen supplementation (days) and non-invasive ventilation (days) will be compared between treatment groups by using the Mann-Whitney U-test.• Acid-base balance parameters (i.e. pH, pCO₂, pO₂, HCO₃, BE, lactate) will be summarized by treatments group as absolute and change from pre-treatment values by means of descriptive statistics.

LIST OF ABBREVIATIONS AND DEFINITION OF TERMS

ADE	Adverse Device Effect
ADR	Adverse Drug Reaction
AE	Adverse Event
APGAR	Appearance, Pulse, Grimace, Activity, Respiration
ATC	Anatomical Therapeutic Chemical classification
BiPAP	Bi-level Positive Airway Pressure
BPD	Bronchopulmonary Dysplasia
BSID	Bayley Scales of Infant Development
BE	Base Excess
BW	Birth Weight
CI	Confidence Interval
CIOMS	Council for International Organizations of Medical
CMH	Cochran-Mantel-Haenszel test
CPAP	Continuous Positive Airway Pressure
CRA	Clinical Research Associate
CRO	Clinical Research Organization
CTS	Clinical Trial Supply
DBP	Diastolic Blood Pressure
DPPC	Dipalmitoylphosphatidylcholine
eCRF	electronic Case Report Form
EC	Ethics Committee
ETT	Endotracheal Tube
FiO₂	Fraction of inspired Oxygen
FIP	Focal Intestinal Perforation
GA	Gestational Age
GCP	Good Clinical Practice
HCO₃⁻	Bicarbonates
HFOV	High Frequency Oscillatory Ventilation
HR	Heart Rate
ICH	International Conference on Harmonization
IFU	Instructions For Use
IIT	Investigator Initiated Trial
IRB	Institutional Review Board
IND	Investigational New Drug Application
IRT	Interactive Response Technology
ISMB	Independent Safety Monitoring Board
ITT	Intention to Treat
IVH	Intraventricular Hemorrhage
IVRS	Interactive Voice Response System
IWRS	Interactive Web Response System

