6.5 Treatment allocation

A balanced block randomization scheme stratified by investigational site and gestational age group (i.e. from 25⁺⁰ to 26⁺⁶ weeks and from 27⁺⁰ to 28⁺⁶ weeks) will be prepared via a computerized system. Once the neonate’s eligibility to take part in the study is confirmed, neonates will be centrally assigned to one of the two treatment arms (LISA/Poractant alfa or ETT/Poractant alfa) through an IRT system (Interactive Response Technology, combination of voice and web response system and also referred as IVRS/IWRS). Enrollment will be staggered: the gestational age will be restricted to 27⁺⁰ to 28⁺⁶ weeks for at least the first 15 randomized neonates. After ISMB evaluation of safety data from the first 15 neonates, provided no safety concerns are raised, the enrolment will be extended to the whole population (25⁺⁰ to 26⁺⁶ weeks and from 27⁺⁰ to 28⁺⁶ weeks).

The IRT will allocate the subject to a certain treatment group using a list-based randomization algorithm and assign the unique screening number of eight digits: the country will be the first three digits (according to ISO 3166 Numeric Country Code), the investigational site number will be the second two digits and the following three digits will be the progressive numbering of the subject within each site (e.g. for the first USA site the screening numbers will be 84001001, 84001002 etc.). The IRT will also generate a confirmation after every IRT transaction is performed.

The Investigator will call the IRT on admission to receive the subject screening number and randomize the subject and obtain the medication (Poractant alfa) kit numbers. Detailed instructions for use of IRT will be provided to the site.

In the LISA group, the relevant catheter provided by the Sponsor (CHF 6440) will be dispensed and used for administration. In the control group, the endotracheal tubes available at the investigational sites for clinical practice will be used for administration.

The LISA catheter (CHF 6440) will be dispensed by the IRT system.

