12. STATISTICAL METHODS

12.1. Sample Size

No primary efficacy endpoint was defined in this study since the main objective is to describe the overall safety and efficacy profile of administering poractant alfa with two different

procedures: LISA technique or conventional administration with endotracheal tubes and brief invasive ventilation. A total of 150 neonates will be randomized in the study with a ratio 2:1 to LISA arm (i.e. 100) and conventional administration arm (i.e. 50).

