12.3.4. Efficacy variables

Need for mechanical ventilation/intubation

- Percentage of neonates needing invasive mechanical ventilation in the first 72 hours of life, in the first 28 days PNA and within 36 weeks PMA will be compared between group using the Cochran-Mantel-Haenszel (CMH) test adjusted for gestational age group. The CMH adjusted difference with its 95% CI will be presented. Additional analysis will be performed to explore the impact of use of sedation and/or analgesia.
- Percentage of neonates needing any intubation procedure, outside the initial surfactant administration period, in the first 72 hours of life, 28 days PNA and within 36 weeks PMA will be compared between treatments as need for IMV.

SpO₂

- SpO₂ will be analyzed using a linear mixed model for repeated measures (MMRM) including treatment, time point, treatment by time point interaction, and gestational age group as fixed effects and pre-procedure SpO₂ as covariate. The adjusted means in each treatment group, the adjusted mean difference between treatments and their 95% CIs at each time point and averaged over the first 120 hours post-treatment will be estimated by the model. Time profile plot of mean SpO₂ in the first 120 hours post-administration will be presented by treatment group.
- SpO₂ will be summarized by treatments on neonates still receiving respiratory support at 28±2 PNA and 36 weeks PMA by means of descriptive statistics.

FiO₂

- FiO₂ will be analyzed using a linear MMRM including treatment, time point, treatment by time point interaction, and gestational age group as fixed effects and pre-procedure FiO₂ as covariate. The adjusted means in each treatment group, the adjusted mean difference between treatments and their 95% confidence intervals (CIs) at each time point and averaged over the first 120 hours post-treatment will be estimated by the model. Time profile plot of mean FiO₂ in the 120 hours post-treatment will be presented by treatment group.
- FiO₂ will be summarized by treatments on neonates still receiving respiratory support at 28±2 PNA and 36 weeks PMA by means of descriptive statistics.

SpO₂/FiO₂ ratio

- SpO₂/FiO₂ will be analyzed using a linear MMRM including treatment, time point, treatment by time point interaction, and gestational age group as fixed

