- Number of maneuvers discontinued due to neonate's severe destabilization will be summarized by treatment group by means of descriptive statistics.
- Duration of surfactant administration (min) and overall procedure for surfactant administration will be compared between treatment groups by using the Mann-Whitney U- test.

Mortality and BPD

- Death/BPD incidence at 36 weeks PMA will be compared by treatment by means of CMH test, adjusting for GA group and related 95% confidence interval will be provided.

- The incidence of BPD at 36 weeks PMA will be compared by treatment as for Death/BPD incidence.
- The mortality at 36 weeks PMA and at Day 28 will be compared by treatment as for Death/BPD incidence.
- Oxygen use at Day 28 (alone and / or during any kind of MV) will be compared by treatment as for Death/BPD incidence.

Other safety variables

- Feeding and hearing status at discharge or 40 weeks PMA (whichever comes first) will be summarized by treatment group by frequency distributions.
- Weight, OFC and length at discharge home or 40 weeks PMA will be summarized by treatment group by descriptive statistics.
- Neonates needing invasive or non-invasive respiratory support at discharge home or 40 weeks PMA will be summarized by treatment group by frequency distribution
- Neonates needing respiratory medications at discharge home or 40 weeks PMA will be summarized by treatment group by frequency distribution

Health status questionnaire at 24 months (± 3 months) corrected age

(This stand-alone assessment will be analyzed and reported separately from the main phase)

- Bayley Scales of Infant Development (cognitive and language scores) will be summarized using descriptive statistics by treatment group and BSID version (III or IV).
- Vital signs and all other variables collected through the questionnaire (i.e., anthropometric measures, cerebral palsy, seizures, feeding method, functional disability and respiratory morbidity) will be summarized by treatment group by frequency distribution or descriptive statistics, as appropriate.

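### Ventilation and oxygen durations are tested without the gestational-age stratum used elsewhere: valid, but some power is lost if gestational age predicts duration

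*Protocol*

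**What the plan says.** Section 6.5 sets up blocked randomization "stratified by investigational site and gestational age group", with GA groups 25+0 to 26+6 and 27+0 to 28+6 weeks. Section 3 states "Approximately 25 investigational sites will be involved in US", and section 12.1 states "A total of 150 neonates will be randomized in the study with a ratio 2:1 to LISA arm", that is 100 against 50.

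Most model-based or stratified comparisons carry GA group:

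- The CMH tests adjust for it. Section 12.3.4 covers need for invasive ventilation and any later intubation. Section 12.3.5 covers failed first insertion, BPD, mortality, oxygen use at Day 28 and the composite: "Death/BPD incidence at 36 weeks PMA will be compared by treatment by means of CMH test, adjusting for GA group".
- The mixed models for SpO₂, FiO₂ and their ratio include "treatment by time point interaction, and gestational age group as fixed effects".

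The durations do not. Section 12.3.4 says "non-invasive ventilation (days) will be compared between treatment groups by using the Mann-Whitney U-test", in a sentence that also covers invasive ventilation and stand-alone oxygen. The synopsis agrees, listing "Duration of invasive mechanical ventilation in the first 72 hours of life, in the first 28 days PNA and within 36 weeks PMA" under the same test and adding "Duration of stand-alone oxygen supplementation (days) and non-invasive ventilation (days) will be compared between treatment groups by using the Mann-Whitney U-test". No stratum or covariate is named, and no reason is given.

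**The concern.** Need for invasive ventilation and its duration stand in the same section, yet one is analysed within GA group and the other is not. When allocation is balanced within a group that predicts the outcome, the difference between groups cannot contribute much to the difference between arms. An unstratified rank test still counts that difference as noise. Its standard error is then too large for the design, and a real effect is easier to miss.

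Duration of invasive and non-invasive ventilation is named in the secondary objective (section 2.2), and the comparison rests on only 50 control neonates. The protocol names this test outright in two places, so it is not a detail left to the SAP.

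**Working it through.** **No figure to reproduce.** Section 12.1 gives 150 neonates with no effect size, SD or power.

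**Inputs from the protocol.** 100 against 50; two GA groups; about 25 sites, so 25 × 2 = 50 site-by-GA cells and 150 / 50 = 3 neonates per cell; at least the first 15 neonates from the older group (section 6.5).

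**Assumptions.** Log-normal durations with log-SD 1; LISA durations 40% shorter, a shift of −ln 0.6 = 0.511 SD; two-sided 5%; permuted blocks of 3 or 6; after the first 15, 40% of neonates in the younger group; durations in the younger group r times as long.

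**Tests.**
- Mann-Whitney: Z = (W − m(n+1)/2) / √V, with V = mk / [n(n−1)] × Σ(rank − mean rank)², where m and k are the arm sizes and n = m + k.
- Van Elteren: Z = Σ w_h(W_h − E_h) / √(Σ w_h² V_h), with w_h = 1/(n_h + 1), summed over the two GA groups.

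**Hand check (normal theory on log durations, exact 2:1 balance in both GA groups).** With a share p in the younger group, ignoring GA inflates the SD by f = √(1 + p(1−p)(ln r)²). The standard error is √(1/100 + 1/50) = 0.1732, so the standardized effect is 0.511 / 0.1732 = 2.949. Adjusted power is Φ(2.949 − 1.96) = 83.9%. Unadjusted power is Φ(2.949 − 1.96f), and the true type I error is 2Φ(−1.96f). With p = 0.4:

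| r | f | True type I error | Unadjusted power | Loss (points) |
|---|---|---|---|---|
| 1 | 1.000 | 5.0% | 83.9% | 0 |
| 1.5 | 1.020 | 4.6% | 82.9% | 1 |
| 2 | 1.056 | 3.9% | 81.0% | 3 |
| 3 | 1.136 | 2.6% | 76.5% | 7 |
| 4 | 1.209 | 1.8% | 71.9% | 12 |

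**Simulation of the rank tests with incomplete blocks in 25 sites × 2 GA groups.**

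| r | Mann-Whitney power | Van Elteren power | Loss (points) |
|---|---|---|---|
| 1 | 81.5% | 81.3% | 0 |
| 1.5 | 79.6% | 80.1% | about 1 |
| 2 | 77.4% | 81.0% | 3-4 |
| 3 | 73.1% | 81.6% | 8-9 |

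At r = 4 the loss was 14-15 points. With 25% instead of 40% in the younger group it was about 0, 1, 2-3, 6-7 and 10-11 points at r = 1, 1.5, 2, 3 and 4.

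**Type I error.** Because blocks stay incomplete, Mann-Whitney is less conservative than under exact balance: 4.0-4.8% at r = 2 and 2.3-3.9% at r = 4. Van Elteren stayed at 4.6-5.2%.

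**Many zeros (neonates never ventilated).** With 40 against 60% ventilated (LISA against control) in the younger group and 25 against 45% in the older, the loss was 0-1, 1 and 2-3 points at r = 1, 2 and 4. With a strong contrast (50 against 70%, and 15 against 35%), it was 3, 5-6 and 7-8 points.

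**Unequal treatment effects.** If LISA shortens durations only in the younger group (to 0.35 times), Mann-Whitney has the higher power: 52.5 against 48.6% at r = 1.5, and 52.2 against 48.7% at r = 2. With a milder contrast (0.45 times in the younger, 0.75 times in the older), it was 74.4 against 73.3% at r = 1.5 and 72.4 against 73.0% at r = 2; van Elteren led by 6 points at r = 3. If the effect lies only in the older group, van Elteren does better.

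**The case against.** The strongest reply is that nothing here is an error. The test is standard and valid, section 1.1 calls the study explorative, and section 12.1 sets no primary efficacy endpoint and no power to be missed. That stands, and it keeps the point optional.

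A reader might infer that omitting a randomization stratum biases the comparison or inflates false positives. It does not: the simulated type I error was at or below 5% within simulation error, and the departure is in the conservative direction.

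A reader might also infer that the protocol contradicts itself, or that these durations are the only unadjusted comparisons. Neither is supported. The Fisher test on additional surfactant doses (section 12.3.4) and the Mann-Whitney tests on procedure durations (section 12.3.5) also omit GA group, so the pattern may be a choice by type of test.

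The larger losses need durations 3 to 4 times as long in one of two adjacent two-week GA bands, and nothing in the documents establishes that. At 1.5 to 2 times the loss is about 1-4 points. This stands.

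Finally, stratifying might be taken to be free. It is not strictly so: the unequal-effect runs show a cost of about 4 points in the least favourable setting examined.

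**Conclusion.** The point holds as an optional improvement. The protocol fixes an unstratified test for three durations while its design and its CMH and mixed-model analyses use GA group. The planned test is valid. Under an equal 40% reduction with 40% younger neonates, it gives up about 0-1 points of power at a GA ratio of 1-1.5, 3-4 at 2 and 8-9 at 3; for invasive ventilation with many zeros and a modest GA contrast, about 0-3 points. These sizes depend on the assumed GA effect, GA mix, block size and log-normal shape, none of which the documents give. The direction is firm when the treatment effect is similar in both GA groups. It can reverse, by up to about 4 points, when the effect is confined to the younger group and the GA effect is modest. No conclusion of the trial is put at risk.

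**What to change.** In section 12.3.4 and the synopsis, replace the Mann-Whitney U-test for the durations of invasive ventilation, stand-alone oxygen and non-invasive ventilation with: *Wilcoxon rank-sum test stratified by GA group (van Elteren)*. Keep the medians by arm. Stratify by GA group only, as the CMH and mixed-model analyses do, because site-by-GA cells hold about 3 neonates. For consistency, the same wording can be used for the procedure-duration tests in section 12.3.5. The change stops at the test and calls for no new effect measure.

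The cost is wording. GA group is already recorded for randomization, so no data or neonates are added, and type I error is not inflated. If GA does not predict duration, the power cost was at most 0.6 points in the settings simulated with an equal effect in both groups. The remaining price is the possible loss of about 4 points described above.
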